## LIST OF ABBREVIATIONS

ANSM: Agence Nationale de Sécurité du Médicament [French National Agency for Medicines and Health Products Safety]

ISC: Intermittent Self-Catheterisation

GCP: Good Clinical Practices

EC: Ethics Committee

CNIL: Commission Nationale Informatique et Libertés [French Data Protection Authority]

CPP: Comité de Protection des Personnes [Ethics Committee]

CRF or eCRF: electronic case report form

CRO: Contract Research Organization

CSP: Code de la Santé Publique [French Public Health Code]

MD: Medical Device

AE: Adverse Event

SAE: Serious Adverse Event

USAE: Unexpected Serious Adverse Event

GENULF: Groupe d'Études de Neuro-Urologie de Langue Française [French Neuro-Urology Study Group]

I-CAS: Intermittent Catheterisation Adherence Scale

I-CAT: Intermittent Catheterisation Acceptance Test

IC-Di-Q: Intermittent Catheterisation Difficulty Questionnaire

SC: SpeediCath

1 SYNOPSIS

Title	STUDY OF SPEEDICATH CATHETER SELECTION CRITERIA AT THE START OF SELF-CATHETERISATION
Short title	Eva
Sponsor	COOPLAST
Coordinator	[name]
Trial type	Multicentre observational study
Objectives	
Primary objective:          Specify the final choice criteria for the type of SpeediCath (SC) catheter that provides patient satisfaction determined by self-questionnaire at V3
 
Secondary objectives:
 
 
- Document the reasons for the patient's initial choice of the SC catheter: determined by self-questionnaire at V1
 
- Determine the patient's adherence to Intermittent Self-Catheterisation (ISC) at the end of follow-up and his/her development over the first six months: measured by I-CAS at V2 and V3
 
- Document patient satisfaction with the catheter: measured on a five point scale at V2 and V3
 
- Document challenges during the first six months of the ISC: measured by the IC-Di-Q at V2 and V3
 
- Determine the variables associated with the catheter selection and adherence to the ISC.
 

Eligibility criteria	
Inclusion criteria
 
 
• Female or male aged eighteen years or older
 
• Subject informed of the study and who decided to participate in it (non-opposition)
 
• Subject affiliated with a social security scheme or beneficiary
 
• Subject with neurogenic or non-neurogenic bladder issues, justifying the implementation of ISC to empty the bladder
 
• Subject who received his/her initial ISC training at the time of inclusion
 
• Subject for whom the expected ISC duration is at least six months
 
• Subject for whom at least two types of SC catheters have been introduced and who has chosen to use the catheters from the SpeediCath range as the first catheter for self-catheterisation
 
• Subject able to independently conduct ISC
 
• Subject for whom the healthcare professional has recommended to conduct ISC at least four times per day
 

	Exclusion criteria 
 
• Vulnerable subject with regard to the current regulation
 
• Pregnant, parturient or breast-feeding woman;
 
• Subject deprived of freedom by judicial, medical or administrative decision;
 
• Under age subject;
 
• Subject legally protected or unable to express consent
 
• Subject not affiliated with or not a beneficiary of a social security scheme;
 
• Subject falling into several categories above;
 
• Subject who refused to participate in the study
 
• Subject participating in an interventional clinical study
 
• Subject who, according to the investigator, has cognitive problems that prevent him/her from completing a questionnaire or for whom the assessment may be a problem.
 

Implementation of the study	
The study will be offered to all adult subjects with neurogenic or non-neurogenic bladder issues, newly initiated at ISC and users of catheters from the SpeediCath range.
 
The study will be conducted in three visits (inclusion visit, visit between 3 and 12 weeks, visit at 6 months) during which investigators will collect data specific to the self-catheterisation methods and to the use of catheters from the SpeediCath range, as well as a set of patient questionnaires. In the case of a catheter change during follow-up, the model and brand of the new catheter will be documented and the participant will continue the study.

Number of patients needed	250 patients
Study duration	
Duration of inclusion period: 6 months
 
Total study duration: approximately 12 months

Statistical analysis	A statistical analysis plan will be written after approval of the protocol. This document will have a reference value for the statistical analyses.

2 STUDY FLOWCHART

V1 - Screening Visit – Inclusion D0		
	Investigator	Patient information
		Inclusion and non-inclusion criteria
		Socio-demographic data
		Clinical data and scores
		Acceptance of the ISC (I-CAT)
		Concomitant bladder treatments
		Method for choosing the catheter and the patient's criteria for choosing the catheter
		Education conditions and ISC methods
		Adverse events
V2 - Follow-up visit - 3 to 12 weeks		
	Investigator	Clinical data
		Continuation of ISC
		Continued use of chosen catheter
		Concomitant bladder treatments
		Adverse events
	Patient	Daily frequency of the ISC
		Overall impression with the ISC
		Satisfaction with the catheter (on a five point scale)
		Challenges during the ISC (IC-Di-Q)
		ISC adherence (I-CAS)
V3 - End of study visit – around 6 months		
	Investigator	Clinical data
		Continuation of ISC
		Continued use of chosen catheter.
		Concomitant bladder treatments
		Adverse events
	Patient	Daily frequency of the ISC
		Overall impression with the ISC
		Satisfaction with the catheter (on a five point scale)
		Patient's final choice criteria for the catheter
		Challenges during the ISC (IC-Di-Q)
		ISC adherence (I-CAS)

### 3 STUDY RATIONALE

Urinary self-catheterisation involves emptying your bladder on your own by inserting a catheter into the urethra. This is the standard method in the case of dysfunctions of the **bladder** clean-out phase, **particularly in the case of complete urinary retention or complete or incomplete bladder clean-out with subvesical obstruction**. Neurological conditions such as spinal cord injuries, multiple sclerosis, multiple system atrophy, peripheral neuropathies, or Parkinson's disease and stroke can cause bladder disturbances. These disturbances can also result from pelvic denervations that are consequences of extended pelvic surgeries or radiation therapy intended for the treatment of gynaecological, urological or digestive cancers.

The goal of ISC implementation is to reduce the morbidity related to vesico-sphincter dysfunction and improve the quality of life of patients by making them more independent.

It involves for the patient a rigorous learning phase and an acceptance phase of this new micturition mode.

When intermittent self-catheterisation (ISC) is indicated, training is provided to the patient in order to enable him/her to manage the catheterisation on a daily basis. The objectives of this study are to understand, achieve, monitor and adapt self-care. This training, primarily provided by the nursing staff and/or a specialist doctor, is usually ensured during an admission to hospital. After returning home, the patient continues to be monitored by the specialist doctor and the nursing team to assess the mastery of the technique (possibly review the procedure and ensure the suitability of the catheter), patient adaptation to ISC practice, his/her compliance with the associated rules (frequency and regularity of catheterisations, urine volume) and any complications. A first visit is usually performed between three and twelve weeks, then a second visit after six months of use.

But this patient therapeutic education (PTE), even performed by experienced and specifically trained staff, may not be sufficient for the patient's immediate acceptance and his/her adherence to self-catheterisation in the medium or long term.

It is indeed appropriate for the patient to be a participant in his/her choice, at least for the equipment, since it is usually up to the doctor to decide on self-catheterisation and that the benefits of self-catheterisation outweigh the constraints. The patient should therefore be guided and involved in the choice of his/her catheter during this learning phase, ensuring better compliance and future adherence to the treatment.

The interest of this study is therefore to better understand the patient's true motivations in choosing the catheter. This will likely allow for improvements in the future, either the equipment itself or certain PTE sequences, with a focus on problematic points or questions in terms of the choice of the catheter offered to the patient by the healthcare staff. The determinants of the patient's choice are all the more important as there are a very large number of catheters on the market.

That is how Coloplast offers a range of SpeediCath® (SC) self-lubricated ready-to-use hydrophilic catheters. This range is designed to cover different patient needs, providing catheters with different lengths, flexibility, shapes and ergonomics. There are three types of catheters adapted to women (SC Standard®, SC Compact® and SC Compact Set, SC Compact Eve®), and three types of catheters adapted to men (SC Standard®, SC Compact® and SC Compact Set, SC Flex®).

With regard to technical specificities, a systematic review of the literature concluded that hydrophilic catheters (with a lubricant attached to the catheter) provided a benefit, in terms of safety and quality

of life, particularly in patients with spinal cord injuries. SC® catheters significantly reduce trauma to the urinary tract by reducing friction. Another study also showed that the implementation of SpeediCath catheters was significantly faster, convenient and discrete, compared to a non-ready-to-use hydrophilic catheter (need to activate the lubricant). The superiority of SpeediCath Compact Male and Female catheters in terms of quality of life compared to reference catheters was demonstrated in a randomised study using the validated specific ISC-Q questionnaire and was retained and valued by CNEDiMTS.

To date, there is no objective data to help in the choice of the type of catheter to offer to the patient based on his/her needs. Although it is now known that the quality of life of patients practising ISC is dependent on multiple factors, there is little data on factors that facilitate or hinder adherence to ISC during the first six months, post-initiation to ISC. The exploratory multicentre prospective observational study we want to conduct aims to determine which criteria are the patient's choice in terms of SC catheters. This information would allow in the future to be able to implement personalised advice with each patient, with the aim of offering them the SC catheter that best suits his/her needs. The study population will consist of adults with neurogenic or non-neurogenic bladder issues justifying the implementation of ISC, with ISC education occurring at the time of inclusion. Patients should be independent in the practice of ISC, and the minimum expected duration of follow-up should be greater than or equal to six months. Only patients who choose to use catheters from the SpeediCath range will be included in the study.

Many criteria will be collected to allow for a thorough analysis of the methods for choosing the type of SC catheter. This collection involves the use of patient self-questionnaires. These questionnaires will be collected during the patient's usual follow-up, including a visit at the time of ISC education, a follow-up visit around three to twelve weeks (depending on the investigator site practices) and a second follow-up visit around six months.

- ✓ ISC acceptance will be measured by the "Intermittent Catheterisation Acceptance Test" (I-CAT) questionnaire. This is a patient questionnaire developed by the French Language Neuro-Urology Study Group (GENULF) and validated in French in 2016 in a multicentre prospective study conducted in 201 neurological and non-neurological patients. The I-CAT helps to better assess and understand the psychological barriers that patients face in relation to ISC. The questionnaire consists of fourteen questions, with a minimum score of 0 for perfect acceptance, and the maximum score of 56 characterises the worst possible acceptance.
- ✓ The difficulties experienced by patients during the ISC will be measured by the Intermittent Catheterisation Difficulty Questionnaire IC-Di-Q. This is a patient questionnaire validated in French, and aims to assess the difficulties encountered during the performance of the ISC. It explores in thirteen questions many factors such as pain, blockage, bleeding, spasticity, urethral sphincter spasm, in terms of frequency of occurrence and intensity. The purpose of this questionnaire is to identify the challenges faced by patients, and to follow up their progress after alternatives or solutions have been put in place (including adapting to the type of catheter).
- ✓ Patient adherence or compliance to the ISC will be measured by the Intermittent Catheterisation Adherence Scale (I-CAS). This is a patient questionnaire validated in French consisting of eight questions, seven of which have a binary answer (yes/no) and one has five proposed responses. The score ranges from 0 for strong ISC adhesion to 8 for very low adhesion.

- ✓ A study-specific self-questionnaire was also created with the support of the scientific council to determine the reasons for the patient's choice of the catheter. This questionnaire includes the patient's independent criteria (e.g. nurse's advice) and patient-specific criteria (e.g. ease of use, discretion).

## 4 STUDY OBJECTIVES

The purpose of this exploratory study is to determine the major criteria in the choice of catheter by patients.

The results will allow for personalised counselling to be put in place for each patient, in order to offer him/her as a first-line treatment the catheter that is the most appropriate for his/her profile, with the goal of facilitating ISC learning and improving ISC adherence and acceptance.

### 4.1 Primary objective

The primary objective of this study is to specify the final criteria for choosing the SC catheter that provides patient satisfaction, as determined by self-questionnaire at V3.

### 4.2 Secondary objectives

The secondary objectives are as follows:

- Document the criteria for the patient's initial choice of the SC catheter: determined by self-questionnaire at V1
- Document patient satisfaction with the SC catheter: measured on a five point scale at V2 and V3
- Document the challenges encountered during the first six months of the ISC: measured by the IC-Di-Q at V2 and V3
- Determine patient adherence to the ISC over the first six months: measured by I-CAS at V2 and V3.
- Determine the variables associated with the catheter selection and adherence to the ISC.

## 5 METHODOLOGY

This is a prospective, multicentre, descriptive, observational, cohort study of routine care.

This research does not involve any additional risk to current practice and minimal constraints related to the conducting of questionnaires. All care procedures will be performed and the products used in the usual way.

### 5.1 Study Devices

#### General information

SpeediCath® is a range of four types of urinary catheters, available as different products with different sizes and also marketed in sets (pre-connected to bags). These are class 1 sterile devices with CE marking intended to be introduced into the urethra to clean out the bladder. This range is developed and manufactured by Coloplast A/S, 3050 Humlebaek, Denmark.

Product	First year of marketing
SpeediCath standard®	2000
SpeediCath Compact® Female	2005
SpeediCath Compact® Male	2011
SpeediCath Compact Eve®	2015
SpeediCath Flex ®	2017

The products from the SpeediCath® range will be used according to the indication provided and described in the instructions for use. The patient will follow his/her healthcare professional's recommendations for the ISC methods.

### Description

The SpeediCath® range is a range of ready-to-use, self-lubricating hydrophilic catheters designed to meet all patient needs. It includes products for men and others for women. The main difference lies in the length of the catheter, adapted to the male and female anatomies. The products used in this study are the following:

- SpeediCath Standard is a standard 40 cm catheter for men and 20 cm for women. It also exists in 30 cm for adolescents.
- SpeediCath Compact is a catheter that helps improve convenience and discretion. It can be done by no-touch insertion of the catheter and is available for both men and women.
- SpeediCath Compact Eve is a female catheter only. It has a triangular shape that makes it easy to handle.
- SpeediCath Flex is a flexible catheter with a sealable sheath and multi-directional olive-shaped tip for easy insertion: it only exists for men.

SpeediCath Compact catheters also come in a set (already connected to a bag).

## Handling

All subjects will be trained by the healthcare team to use the products according to current recommendations.

### 5.2 Duration of patient follow-up

The follow-up of participants in this study will be six months after ISC implementation and learning.

### 5.3 Planned total study duration

The total expected duration of the study is twelve months, with an inclusion period of six months and a follow-up period of six months.

### 5.4 Managing potential bias

#### 5.4.1 Blinding

This is an open-label study of the management of ISC, therefore blinding is not applicable.

#### 5.4.2 Bias

Not applicable

## 6 STUDY POPULATION

### 6.1 Participants

The study population will consist of adults with neurogenic and non-neurogenic bladder issues, newly initiated at ISC, and users of catheters from the SpeediCath range.

### 6.2 Eligibility criteria

#### 6.2.1 Inclusion criteria

- Female or male aged eighteen years or older
- Subject informed of the study and who decided to participate in it (non-opposition)
- Subject affiliated with a social security scheme or beneficiary
- Subject with neurogenic or non-neurogenic bladder issues, justifying the implementation of intermittent self-catheterisation (ISC) to clean out the bladder
- Subject who received his/her initial ISC training at the time of inclusion
- Subject for whom the expected ISC duration is at least six months
- Subject for whom at least two types of SC catheters have been introduced and who has chosen to use the catheters from the SpeediCath range as the first catheter for self-catheterisation
- Subject able to independently conduct ISC
- Subject for whom the healthcare professional has recommended to conduct ISC at least four times per day

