## 8 COLLECTED DATA

### Screening and inclusion visit

During this visit, the following data will be recorded in the case report form:

- Unique identifier number;
- Date of visit;
- Patient's socio-demographic data: gender, age, living alone or with someone, professional activity, level of education
- Patient's clinical data: pathology and degree of involvement, history (age of bladder issues, bladder clean out mode, urinary symptoms (USP score), concomitant bladder treatments), anorectal dysfunction (considering the impact of these disorders on vesico-sphincter balance), accessibility of urinary meatus (manual dexterity, upper limb joint range of motion, mobility, limitation of lower limb abduction in women, vision disorders, obesity, overweight with significant apron belly, prolapse in women), urethral sensitivity (normal/decreased/increased)

- Acceptance questionnaire for I-CAT ISC
- Choice of catheter: catheters presented by the nurse, catheters tried by the patient, SpeediCath (SC) catheter chosen by the patient as the first catheter for self-catheterisation and the criteria that presided over this choice
- ISC learning terms and conditions: location, duration, number of trainings in the procedure, prescription of home nursing representative
- Recommended frequency for ISC
- ISC alone or associated with spontaneous urination
- Possible adverse events
- Date of next visit

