## 9.2 Statistical analysis

The analyses will be performed using the SAS V9.4 software (or earlier version), on a frozen database, after review of data allowing to identify protocol deviations and their potential impact on the analysis criteria. Protocol deviations will be classified as minor or major. Major deviations will lead to the exclusion of patients from the per protocol (PP) population. The distribution of patients in the analysis populations will be reviewed and approved by the sponsor before the database freeze.

The description of all the parameters will be based on the type of catheter and according to the gender of the patients. Quantitative parameters will be described using the following statistics: number of non-missing data, mean, standard deviation, median, first and third quartile, minimum and maximum. Qualitative parameters will be described using the headcounts and the percentages. These will be calculated from the number of non-missing observations. In all cases, the number of missing data will be specified.

Univariate analyses then multivariate analyses by logistic regressions will be performed to identify, among the data studied (patient choice criteria at V1, his/her final choice at V3, his/her adherence to ISC, his/her satisfaction with the catheter, his/her challenges during ISC, his/her clinical and socio-demographic characteristics, etc.), the predictive factors of the final choice of the SpeediCath catheter (Standard, Compact or Flex for male patients; Standard, Compact or Compact Eve for female patients).

The same will be done for adherence to ISC at V3 (with clinical and socio-demographic characteristics at V1, I-CAT score at V1, ICDQ score at V2, type of catheter chosen).

The other secondary endpoints will be described at the different time points and according to the catheter type.

Missing data at the time of analysis will not be replaced and will be considered as such.

A statistical analysis plan will be written after approval of the protocol. This document will have a reference value for the statistical analyses.

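### The final-choice analysis does not say how it will account for patients shown only two of the three SpeediCath types for their sex

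*Protocol*

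**What the plan says.** Four parts of the protocol bear on this.

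- **Eligibility (section 6.2.1, repeated in the synopsis).** The floor is two types: "Subject for whom at least two types of SC catheters have been introduced". No rule says which two, or when the third is shown as well.
- **Range (section 3).** "There are three types of catheters adapted to women", and likewise "three types of catheters adapted to men".
- **Analysis (section 9.2).** Logistic regressions look for predictors of the final choice, whose categories are "Standard, Compact or Flex for male patients; Standard, Compact or Compact Eve for female patients". The candidate factors include the V1 choice criteria, adherence, satisfaction, difficulties and "his/her clinical and socio-demographic characteristics, etc". The types presented are not named. The section also describes all parameters by catheter type and sex.
- **Data (section 8).** The inclusion visit records "catheters presented by the nurse, catheters tried by the patient". The V2 and V3 lists record whether the catheter was kept or changed. They have no item on further types introduced to a patient who did not change.

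Section 4.2 makes the variables associated with catheter selection a secondary objective, and section 4 calls the study exploratory. Section 5.4.2, on bias, is marked not applicable.

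**The concern.** A man shown only Standard and Compact cannot pick Flex at V1. In the three-category outcome he looks the same as a man who saw Flex and rejected it. If showing were unrelated to the patient, this would lower the share of the less-shown type but would create no false predictor. If showing depends on a trait, that trait predicts choice even when it has no bearing on preference. Section 8 collects manual dexterity, upper-limb range of motion, mobility and vision. These are clinical characteristics that section 9.2 may test, and they are also plausible reasons to present one type rather than another. That link is an inference; the protocol does not state it.

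Sections 3 and 4 intend the results to support personalised advice on the first catheter. A predictor that reflects presentation practice would then be passed on as if it were patient preference.

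**Working it through.** **The plan's own figures.** Section 9.1 uses n = z²p(1−p)/d² with z = 1.96. For p = 5% and d = 2.75% this gives 241; for p = 50% and d = 6.25% it gives 246. Both match the table. With 250 patients the half-widths are ±2.70 and ±6.20 points. With 225 (10% loss) they are ±2.85 and ±6.53 points. These figures concern the frequencies of choice criteria and are not affected by this point.

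**Inputs for the check.** From the protocol: three types per sex, at least two shown, outcome measured at V3. Assumed, because the protocol gives no figures: equal preference (1/3 each among patients who can choose all three), the showing rates, and the share r of patients not shown a type at V1 who gain access to it by V3.

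**Effect on shares.** If a fraction q of patients is not shown type C, its observed share is (1 − q + qr)/3.

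| q | r = 0 | r = 0.5 |
|---|---|---|
| 0% | 33.3% | 33.3% |
| 25% | 25.0% | 29.2% |
| 50% | 16.7% | 25.0% |

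At q = 50% and r = 0 the shortfall is 33.3 − 16.7 = 16.7 points (unrounded 1/3 − 1/6). For comparison, take 112 evaluable patients of one sex (225 split evenly, an assumption). The 95% half-width at 16.7% is then 1.96 × √(0.167 × 0.833/112) = 6.9 points. More patients would shrink the interval but not the shortfall.

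**Effect on a predictor.** Let a trait have no effect on preference, and let C be shown to a fraction s₁ of patients with the trait and s₀ without it. Then P(C) = [s + (1 − s)r]/3 in each group, and the odds ratio follows.

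| s₁ vs s₀ | r = 0: P(C) | OR | r = 0.5: P(C) | OR |
|---|---|---|---|---|
| 80% vs 40% | 26.7% vs 13.3% | 2.36 | 30.0% vs 23.3% | 1.41 |
| 90% vs 60% | 30.0% vs 20.0% | 1.71 | 31.7% vs 26.7% | 1.27 |
| 70% vs 50% | 23.3% vs 16.7% | 1.52 | 28.3% vs 25.0% | 1.19 |
| equal rates | equal | 1.00 | equal | 1.00 |

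First row, r = 0: (0.267/0.733)/(0.133/0.867) = 2.36. First row, r = 0.5: the access rates are 0.8 + 0.2 × 0.5 = 0.9 and 0.4 + 0.6 × 0.5 = 0.7, so (0.300/0.700)/(0.233/0.767) = 1.41.

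The r = 0 figures assume that everyone shown C saw all three types. If they saw C and one other, half would choose C. The three odds ratios would then be 2.67, 1.91 and 1.62.

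**The case against.** The strongest reply is that section 9.2 defers to a SAP, which is not available here, and that covariate lists and sensitivity analyses are normally settled there. The factor list ends in an open et cetera, the presented and tried catheters are collected, and nothing forbids using them. This largely stands: the point is a repairable omission, not a contradiction. What remains is that section 9.2 already fixes the outcome categories without reference to the set shown. A SAP also cannot recover data on types introduced after V1 that were never collected.

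Second, staff influence is captured: "This questionnaire includes the patient's independent criteria (e.g. nurse's advice"). That records advice as a reason for choosing. It does not identify a type the patient never saw, although the V1 record of catheters presented does.

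Third, the modelled outcome is at V3, and section 7.2 lets patients change catheter freely. This stands and weakens the effect, as the r = 0.5 columns show, but does not remove it.

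A reader might infer more: that the plan deliberately treats all three types as open to everyone, that staff are known to select by patient profile, or that the primary objective is compromised. The documents support none of these. Section 9.2 lists outcome categories and makes no claim about availability. No showing rates or presentation rules are given. The primary objective is the frequency of self-reported final choice criteria at V3, which lies largely outside this problem.

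**Conclusion.** The concern holds in a limited form. Two of three types are enough for inclusion, the final-choice model spans three, and the plan does not say how the recorded set shown will be used. The predictors of final choice and the shares by type may therefore partly reflect presentation.

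The size cannot be determined from the protocol. There is no bias if all patients see all three types, and no spurious trait odds ratio if showing is unrelated to the trait. Under the assumed differential rates, the spurious odds ratio runs from 1.52 to 2.36 with no later access and from 1.19 to 1.41 with half gaining access by V3. These are illustrations that rest on equal preference and assumed rates; they do not estimate what this study will show. The sample size and its precision table are unaffected.

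**What to change.** Keep the inclusion criterion, since the study follows routine care. In section 9.2 (or the SAP, if still open), state that the final-choice analysis will account for the types presented at V1:

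1. Report choice shares by set presented, two types versus all three.
2. Repeat the final-choice regression in patients shown all three types.
3. Optionally, add a choice-set-conditional logistic model as a further sensitivity analysis. It should not be the main model, because the V1 set may no longer be the set available at V3.

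Add one eCRF item at V2 and V3 recording any further type introduced since V1.

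The cost is a few sentences and one data item per follow-up visit; the V1 data are already planned. The intervals will be wider, possibly much wider if few patients of a given sex were shown all three types. The set shown may also partly reflect the patient's own wishes, so conditioning on it does not isolate preference. These analyses should support the main one and not replace it.
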